1.4 Summary of Clinical Experience

No clinical studies have been conducted with MedImmune's RSV sF antigen or with MEDI7510. This is a first time in human (FTIH) study.

There are no approved RSV vaccines for either adults or children. Vaccines consisting of purified F protein alone and in combination with other antigens or with adjuvants have been studied in adults with antigen doses as high as 100 µg. These studies have demonstrated the immunogenicity of the F protein, with antibody responses most likely to be observed in those with low prevaccination titers. There have been no significant safety concerns with RSV F vaccines, although local site reactions have generally been higher in active than placebo arms ([Falsey and Walsh, 1996](#); [Falsey and Walsh, 1997](#); [Langley et al, 2009](#); [Glenn et al, 2013](#)). Clinical efficacy has not been demonstrated for any of these vaccines. Although MEDI7510 is an RSV F subunit vaccine, none of these vaccines is similar to MEDI7510.

GLA-SE is a component of multiple investigational vaccines, but available safety data are limited. In a clinical trial of 1 µg GLA with 2% SE in combination with a recombinant pandemic H5N1 influenza antigen in healthy adults 18 to 49 years of age, higher geometric mean titers (GMTs) of antibody were achieved with lower doses of antigen in the presence of GLA-SE. The influenza antigen in combination with GLA-SE resulted in increased rates of injection site pain and/or tenderness, but most complaints were mild to moderate in intensity ([Treanor et al, 2013](#)).

1.5 Rationale for Conducting the Study

RSV causes significant morbidity in older adults, but there is no specific treatment or prevention strategy available for this population. Palivizumab, a monoclonal antibody (mAb) targeting the RSV F protein, is available only for specified groups of infants, and aerosolized ribavirin, a treatment with unclear efficacy, is not approved for adult use. MEDI7510 is designed to fill the unmet medical need by preventing symptomatic respiratory disease caused by RSV in older adults.

The goal of this FTIH study is to evaluate the safety and tolerability of single ascending intramuscular (IM) doses of RSV sF antigen and of MEDI7510 in adults ≥ 60 years of age who are healthy or who have stable, chronic underlying medical conditions, and to determine if any of these doses result in both humoral and cellular immunity. A single fixed dose of GLA-SE is used in this study so that the immunogenicity of single ascending doses of RSV sF can be assessed in the presence of adjuvant and the contribution of GLA-SE to the immunogenicity of RSV sF can be assessed. Escalating doses of GLA-SE will be evaluated

in a subsequent Phase 1b study to maximize the extent and duration of neutralizing antibody and cellular immune responses to RSV in older adults. This selected dosage level will subsequently be assessed for efficacy against RSV-confirmed respiratory illness.

1.5.1 Risk-benefit Assessment

There are no data on the human safety profile of RSV sF or MEDI7510. Limited clinical data exist for GLA-SE in combination with an influenza antigen in a younger population, in which GLA-SE was associated with increased reactogenicity. Nonclinical toxicology studies of MEDI7510 did not identify any MEDI7510-related safety concerns other than self-limited local reactogenicity. The important potential risks outlined in the development risk management plan (dRMP; also see Section 5.4 of the Investigator's Brochure) are based primarily on the common safety risks observed with injectable vaccines. These potential risks include, but are not limited to, allergic reactions (including anaphylaxis) and severe injection site reactions. Autoimmune and autoinflammatory disorders were not observed in toxicology studies but are a theoretical risk of any adjuvanted vaccine. The risk of developing such conditions with RSV sF or MEDI7510 is unknown.

Subjects will be monitored for important potential risks in MEDI7510 clinical trials, and routine pharmacovigilance and risk minimization activities will be performed.

There are no current preventive or therapeutic strategies for RSV in older adults. The possibility of benefit from participating in this study is unknown, and benefit will not be assessed in this study. It is possible that some subjects in this study might receive a vaccine that has some level of efficacy against RSV disease. Efficacy of MEDI7510 has been demonstrated in experiments in which vaccinated animals have been protected from RSV disease.

1.6 Research Hypotheses

1.6.1 Primary Hypothesis

The primary hypothesis of this study is that administration of single ascending IM doses of the RSV sF antigen or MEDI7510 will be safe and well tolerated in adults ≥ 60 years of age who are healthy or who have stable, chronic underlying medical conditions.

1.6.2 Secondary Hypotheses

The secondary hypotheses are that the administration of single ascending IM doses of RSV sF or MEDI7510 will result in dose-dependent humoral immune responses in adults ≥ 60 years of age who are healthy or who have stable, chronic underlying medical conditions,

and that MEDI7510 will induce cell-mediated immunity greater than that observed with RSV sF alone.

2 OBJECTIVES

2.1 Objectives

2.1.1 Primary Objective

The primary objective of this study is to assess the safety and tolerability of a single ascending IM dose of RSV sF or MEDI7510 in adults ≥ 60 years of age who are healthy or who have stable, chronic underlying medical conditions.

2.1.2 Secondary Objectives

The secondary objectives of this study are:

1. To assess the humoral immune responses to RSV F following immunization with RSV sF or MEDI7510
2. To assess the cell-mediated (T-cell) immune responses to RSV F following immunization with RSV sF or MEDI7510

2.1.3 Exploratory Objective

The exploratory objective of this study is to further assess immune responses to RSV sF and MEDI7510 using exploratory assays.

2.2 Study Endpoints

2.2.1 Primary Endpoint

The primary endpoint is the safety and tolerability of single ascending doses of RSV sF and MEDI7510 as assessed by the occurrence of all solicited symptoms (whether or not treatment emergent) and treatment-emergent adverse events (AEs), serious adverse events (SAEs), new onset chronic diseases (NOCDs), and adverse events of special interest (AESIs) as follows:

- The proportion of subjects experiencing each solicited symptom from administration of investigational product (Day 1) through Day 7 post vaccination (7 days)
- The proportion of subjects experiencing each AE from administration of investigational product (Day 1) through Day 28 post vaccination (28 days)
- The proportion of subjects experiencing each SAE from administration of investigational product (Day 1) through Day 28 post vaccination (28 days)

- The proportion of subjects experiencing each SAE from administration of investigational product (Day 1) through Day 360 post vaccination (360 days)
- The proportion of subjects experiencing each NOCD from administration of investigational product (Day 1) through Day 360 post vaccination (360 days)
- The proportion of subjects experiencing each AESI from administration of investigational product (Day 1) through Day 360 post vaccination (360 days)

2.2.2 Secondary Endpoints

The secondary endpoints relate to the immunogenicity of RSV sF and MEDI7510 as follows:

1. Humoral immunity endpoints

- Post-dose GMTs and post-dose geometric mean fold rises (GMFRs) from baseline in RSV A neutralizing antibody on Days 29, 61, 91, 181, 271, and 361
- The proportion of subjects who experience a post-dose seroresponse to RSV on Days 29, 61, 91, 181, 271, and 361 as measured by neutralizing antibody to RSV A, with seroresponse defined as a ≥ 4 -fold rise from baseline
- Post-dose GMTs and GMFRs from baseline of anti-F immunoglobulin G (IgG) antibodies as measured by an anti-F IgG assay derived from an RSV-specific 4-plex Meso Scale Discovery (MSD; Gaithersburg, MD) assay on Days 29, 61, 91, 181, 271, and 361
- The proportion of subjects who experience a post-dose seroresponse to RSV on Days 29, 61, 91, 181, 271, and 361 as measured by anti-F IgG assay, with seroresponse defined as ≥ 4 -fold rise from baseline

2. Cellular immunity endpoints

- Post-dose geometric mean counts (GMCs) and GMFRs from baseline of RSV F peptide pool interferon gamma (IFN γ) ELISPOT responses on Days 8 and 29
- The proportion of subjects who experience a post-dose cell-mediated immune response to RSV F on Days 8 and 29 as measured by the RSV F peptide pool IFN γ ELISPOT assay

2.2.3 Exploratory Endpoints

Depending on assay availability and the availability of suitable samples, the following exploratory endpoints may be assessed to further evaluate immune responses to RSV:

- The proportion of subjects who experience a post-dose seroresponse to RSV on Days 29, 61, 91, 181, 271, and 361 as measured by palivizumab-competitive enzyme-linked immunosorbent assay (cELISA), with seroresponse defined as ≥ 4 -fold rise from baseline
- Post-dose GMTs and GMFRs from baseline of palivizumab-competitive antibodies as measured by a palivizumab-cELISA on Days 29, 61, 91, 181, 271, and 361

- The proportion of subjects who experience a post-dose seroresponse to RSV on Days 29, 61, 91, 181, 271, and 361 as measured by neutralizing antibody to RSV B, with seroresponse defined as a ≥ 4 -fold rise from baseline
- Post-dose GMTs and GMFRs from baseline of RSV B neutralizing antibodies on Days 29, 61, 91, 181, 271, and 361
- The number of RSV F-specific CD8+ and CD4+ T cells that secrete interleukin 2 (IL-2), IFN γ , tumor necrosis factor alpha (TNF- α), interleukin 4 (IL-4), interleukin 5 (IL-5), and/or other cytokines prior to and post dosing in subjects who received MEDI7510. An exploratory intracellular cytokine flow cytometry assay may be used for these analyses
- The types of cytokines (Th1 vs Th2 vs inflammatory) secreted by RSV F-specific T cells prior to and post dosing in subjects who received MEDI7510. An exploratory Luminex assay for Th1/Th2 cytokines may be used for these analyses

3 STUDY DESIGN

3.1 Description of the Study

3.1.1 Overview

This is a Phase 1a, FTIH, double-blind, randomized, placebo-controlled, cohort escalation study evaluating the safety and tolerability of a single ascending IM dose of RSV sF or MEDI7510 in adults ≥ 60 years of age who are healthy or who have stable, chronic underlying medical conditions. Approximately 144 subjects will be enrolled at approximately 3 study centers in the US and randomized in a 5:1 ratio by cohort to receive a dose of either RSV sF or placebo or MEDI7510 or placebo on Day 1 in ascending doses as follows:

- Cohort 1: 20 μg RSV sF (n = 20) or placebo (n = 4) as a single IM injection
- Cohort 1a: 20 μg MEDI7510 (n = 20) or placebo (n = 4) as a single IM injection
- Cohort 2: 50 μg RSV sF (n = 20) or placebo (n = 4) as a single IM injection
- Cohort 2a: 50 μg MEDI7510 (n = 20) or placebo (n = 4) as a single IM injection
- Cohort 3: 80 μg RSV sF (n = 20) or placebo (n = 4) as a single IM injection
- Cohort 3a: 80 μg MEDI7510 (n = 20) or placebo (n = 4) as a single IM injection

For Cohorts 1a, 2a, and 3a, the indicated dose for MEDI7510 represents the RSV sF dose, and the GLA-SE dose will be fixed at 2.5 μg GLA + 2% (w/v) SE.

Dosing within each cohort will be staggered as described in Section 3.1.2. Cohort escalation will occur after all subjects in the previous cohort(s) are followed for 7 days as described in Section 3.1.3, with parallel cohort progression for Cohorts 1a and 2, and Cohorts 2a and 3 as

described in Section 3.1.3. In addition, cohorts may be expanded to improve safety assessment in accordance with Section 3.1.3.

One interim analysis is planned after all subjects have completed 90 days post dose safety follow-up (Section 4.8.6). This interim analysis will provide safety and immunogenicity data needed to select an antigen dose to include in the Phase 1b study, which will explore GLA-SE adjuvant doses in combination with the selected dose of RSV sF antigen.

Subjects will be in the study for a little more than a year (56 weeks), which includes a screening period of up to 30 days, a treatment period of 1 day, and a 360-day posttreatment safety follow-up period.

A study schematic is shown in Figure 3.1.1-1.

[figure not shown]

Figure 3.1.1-1 Study Flow Diagram

ESMC= external safety monitoring committee; GLA = glucopyranosyl lipid A; IM = intramuscularly; RSV sF = respiratory syncytial virus soluble fusion (protein); SE = squalene emulsion

The endpoints to be measured in this study are described in Section 2.2.

3.1.2 Treatment Regimen

A total of 144 subjects is planned to be randomized at a 5:1 ratio in 6 cohorts to receive a single dose of either RSV sF or placebo or MEDI7510 or placebo administered by IM injection on Day 1 as described in [Table 3.1.2-1](#).

Table 3.1.2-1 Treatment Regimen

Cohort	Number of Subjects	Treatment Regimen
1	24	20 µg RSV sF (N = 20) or placebo (N = 4) as a single IM dose
1a	24	20 µg MEDI7510 (N = 20) or placebo (N = 4) as a single IM dose
2	24	50 µg RSV sF (N = 20) or placebo (N = 4) as a single IM dose
2a	24	50 µg MEDI7510 (N = 20) or placebo (N = 4) as a single IM dose
3	24	80 µg RSV sF (N = 20) or placebo (N = 4) as a single IM dose
3a	24	80 µg MEDI7510 (N = 20) or placebo (N = 4) as a single IM dose

GLA = glucopyranosyl lipid A; IM = intramuscular; RSV sF = respiratory syncytial virus soluble fusion antigen; SE = squalene emulsion; w/v = weight per volume

Note: MEDI7510 comprises RSV sF with 2.5 µg GLA + 2% (w/v) SE; placebo = normal saline

Staggering of Dosing

Within individual cohorts, dosing will be staggered for safety. A minimum of 3 days is required between the initial (N = 5) and final (N = 19) dosing groups of subjects within each cohort.

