3.1.3 Cohort Escalation

A partially parallel cohort progression design will be used for this study, with collection, compilation, and assessment by the External Safety Monitoring Committee (ESMC) of a total of 7 days of safety and laboratory data from the preceding single or concurrent cohorts required prior to enrolling in the subsequent cohort(s). In this schema, Cohort 1 will be enrolled first and all subjects in Cohort 1 will be followed for safety for 7 days prior to enrollment in any subsequent cohort(s). Cohort progression will occur after review of all cumulative safety data, including safety laboratory data (but not including immunogenicity data) by the MedImmune medical monitor, who will review only blinded data, and the ESMC, who will review blinded data and can choose to also review unblinded data. The principal investigators are invited to the open session for blinded review of data. External Safety Monitoring Committee review of cohort progression is described in [Section 4.8.5](#). If there are no safety concerns, Cohorts 1a and 2 may enroll at the same time. After all subjects in those cohorts have been followed for 7 days, Cohorts 2a and 3 will be enrolled in the same

fashion. After all subjects in Cohorts 2a and 3 have been followed for 7 days, Cohort 3a will be completed.

Cohort expansion will occur at the recommendation of the ESMC as described in Section 4.4.1. If cohort expansion occurs, a total of 12 subjects will be added to the expanded cohort with the same randomization ratio (5:1) applied.

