4.2.2.2 Description of Study Procedures, Follow-up

A description of each follow-up study visit and telephone contact is provided below.

Day 3 + 3 (Telephone Contact, T3)

1. Update medical history
2. Assess for all solicited symptoms, and treatment-emergent AEs, SAEs, NOCDs, and AESIs
3. Update all concomitant medications

Day 8 + 3 (Visit, V4)

1. Update medical history, perform targeted physical examination if appropriate
2. Assess for all solicited symptoms, AEs, SAEs, and treatment-emergent NOCDs and AESIs
3. Update all concomitant medications
4. Collect urine for urinalysis (may be collected after phlebotomy)
5. Collect blood samples:

- for serum chemistry and hematology
- for cell-mediated immunogenicity assays

Day 14 + 4 (Telephone Contact, T5)

1. Update medical history
2. Assess for all treatment-emergent AEs, SAEs, NOCDs, and AESIs
3. Update all concomitant medications

Day 29 + 4 (Visit, V6)

1. Update medical history, perform targeted physical examination if appropriate
2. Assess for all treatment-emergent AEs, SAEs, NOCDs, and AESIs
3. Update all concomitant medications
4. Collect urine for urinalysis (may be collected after phlebotomy)
5. Collect blood samples:
 - for serum chemistry and hematology
 - for humoral immunogenicity assays
 - for cell-mediated immunogenicity assay

Day 61 ± 5 (Visit, V7)

1. Update medical history, perform targeted physical examination if appropriate
2. Assess for all treatment-emergent SAEs, NOCDs, and AESIs
3. Assess prohibited concomitant medications
4. Collect serum sample for humoral immunogenicity assays

Day 91 ± 5 (Visit, V8)

1. Update medical history, perform targeted physical examination if appropriate
2. Assess for all treatment-emergent SAEs, NOCDs, and AESIs
3. Assess prohibited concomitant medications
4. Collect serum sample for humoral immunogenicity assays

Day 121 ± 12 (Telephone Contact, T9)

1. Update medical history
2. Assess for all treatment-emergent SAEs, NOCDs, and AESIs
3. Assess prohibited concomitant medications

Day 151 ± 12 (Telephone Contact, T10)

1. Update medical history
2. Assess for all treatment-emergent SAEs, NOCDs, and AESIs
3. Assess prohibited concomitant medications

Day 181 ± 12 (Visit, V11)

1. Update medical history, perform targeted physical examination if appropriate
2. Assess for all treatment-emergent SAEs, NOCDs, and AESIs
3. Assess prohibited concomitant medications
4. Collect serum sample for humoral immunogenicity assays

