4.4.1 Enrollment and Dosing Stopping Criteria

If any of the following events occur, administration of investigational product will be stopped and no additional subjects will be randomized into the study until review by the ESMC.

Events that meet enrolling and dosing stopping criteria 1 through 4 must be reported within 24 hours of knowledge of the event to MedImmune Patient Safety using the Safety Fax Notification Form (see Section 5.6 for contact information). The occurrence of these events does not automatically make an AE serious but, if the consequences of the event are serious, for example, death or hospitalization, the event is serious and must be reported as an SAE (see Section 5.2). These events may or may not be considered to be serious (ie, may or may

not meet criteria for SAEs as described in Section 5.2). Events that might meet enrollment and dosing stopping criteria 5 and 6, particularly investigational product-related Grade 3 or Grade 4 AEs, must first be conveyed to the site monitor and then be entered into the electronic case report form (eCRF) within 24 hours of awareness of the event to trigger reporting to the medical monitor.

1. Death in any subject in which the cause of death is assessed as related to investigational product
2. Anaphylactic reaction related to investigational product in any subject
3. Adverse event of special interest for an adjuvanted vaccine other than new onset or exacerbation of thyroid disorders occurring in any subject enrolled in a cohort dosing with MEDI7510 (RSV sF cohorts may continue dosing and enrolling if this stopping criterion is met)
4. Any SAE assessed as related to investigational product, or any SAE that is not clearly and obviously unrelated to investigational product
5. Any single Grade 4 AE assessed as related to investigational product occurring in any cohort or any two Grade 3 AEs of the same type assessed as related to investigational product occurring in more than one subject in any single cohort
6. Any other safety finding assessed as related to investigational product that, in the opinion of the investigators, the sponsor, or the ESMC might contraindicate further dosing of study subjects

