4.5.1.2 Treatment Administration

The day of dosing is considered Day 1.

All personnel who administer study vaccines must be trained and licensed in accordance with state laws.

All subjects must be safely positioned prior to immunization so that they cannot be hurt in the case of syncope. Topical analgesia may not be applied at the injection site. Investigational product should be administered IM into the deltoid muscle of the upper arm with needle selection according to [Table 4.5.1.2-1](#).

Table 4.5.1.2-1 Injection Site and Needle Size for Intramuscular Injection

Subject Gender/Body Weight	Needle Gauge & Length (Inches)
Male or female 110 to < 130 lbs	22-25 Gauge, 5/8 a
Female 130-200 lbs	22-25 Gauge, 1 - 1½
Male 130-260 lbs	
Female 200+ lbs	22-25 Gauge, 1½
Male 260+ lbs	

IM = intramuscular

^a A 5/8-inch needle may be used for subjects weighing less than 130 lbs (< 60 kg) for IM injection in the deltoid muscle only if the subcutaneous tissue is not bunched and the injection is made at a 90° angle.

Adapted from: <http://www.cdc.gov/vaccines/recs/vac-admin/default.htm>

To administer investigational product (see instructions at <http://www.cdc.gov/vaccines/recs/vac-admin/default.htm>):

- Follow standard administration guidelines for site assessment/selection and site preparation
- To avoid injection into subcutaneous tissue, spread the skin of the selected vaccine administration site taut between the thumb and forefinger, isolating the muscle. Another technique, acceptable for geriatric patients, is to grasp the tissue and “bunch up” the muscle
- Insert the needle fully into the muscle at a 90° angle and inject the vaccine into the tissue
- Withdraw the needle and apply light pressure to the injection site for several seconds with a dry cotton ball or gauze

Additional information about administration of vaccines is available at

http://www.cdc.gov/vaccines/pubs/pinkbook/downloads/appendices/D/vacc_admin.pdf

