4.5.1.3 Monitoring of Dose Administration

Subjects should be observed in the clinic for 30 minutes after vaccine administration. As with any vaccine, allergic reactions to dose administration are possible. Therefore, appropriate drugs and medical equipment to treat acute anaphylactic reactions must be immediately available, and study personnel must be trained to recognize and treat anaphylaxis (Table 8, <http://www.cdc.gov/mmwr/preview/mmwrhtml/rr6002a1.htm#Tab7>; [Kroger et al, 2011](#)). Management of anaphylaxis must be in accordance with current standard of care and clinical guidelines. Vital signs should be repeated between 20 to 30 minutes after dosing.

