4.8.5 External Safety Monitoring Committee

A study-specific ESMC that is advisory to MedImmune will provide ongoing safety surveillance of the study, with regularly scheduled reviews of safety for cohort escalation decisions. This committee will also review data at other timepoints in response to events meeting enrollment and dosing stopping criteria (Section 4.4.1) or events assessed as medically relevant by the medical monitor or one of the site investigators. Details are provided in the ESMC charter.

For cohort escalation decisions, the ESMC and the MedImmune medical monitor will review blinded data by cohort, including all AEs/SAEs, laboratory parameters, and AESIs observed between dosing of the initial subject in the cohort(s) and the time that the final subject enrolled in the cohort(s) has completed 7 days of safety follow-up. Cumulative safety data

for other cohorts will also be reviewed. In addition, the ESMC has the option of reviewing unblinded data but cannot reveal any grouped or unblinded data to blinded MedImmune or site staff. Dose escalation decisions and outcomes of reviews of safety and other relevant data will be communicated to MedImmune. The sponsor will notify sites when enrollment into each dose cohort has been completed and when enrollment into the next dose cohort is permitted. The US FDA and IRBs/IECs will be notified when the ESMC has recommended that study dosing be halted or that cohort escalation should not occur.

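### The within-cohort stagger releases the final 19 subjects on elapsed time alone, so they may be dosed before the initial five have had any scheduled safety enquiry after Day 1

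*Protocol*

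**What the plan says.** - **Stagger (Section 3.1.2).** "A minimum of 3 days is required between the initial (N = 5) and final (N = 19) dosing groups". The section gives safety as the purpose. It attaches no contact, data check or decision to the step from five subjects to 19.
- **Day numbering (Section 4.5.1.2).** "The day of dosing is considered Day 1".
- **Dosing visit (Sections 4.2.2.1 and 4.5.1.3).** "Subjects should be observed in the clinic for 30 minutes after vaccine administration". Vital signs are repeated and symptoms and adverse events are assessed that day.
- **First scheduled contact after that (Section 4.2.2.2, Table 4.2.2-1).** The entry reads "Day 3 + 3 (Telephone Contact, T3", closing the bracket after T3. Its task is: "Assess for all solicited symptoms, and treatment-emergent AEs, SAEs, NOCDs, and AESIs". The window runs forward only. The next scheduled contact, with the first post-dose laboratory tests, is the Day 8 visit, also with a window of plus 3 days.
- **Scheduled reviews (Sections 3.1.3 and 4.8.5).** The External Safety Monitoring Committee (ESMC) and the medical monitor review data to decide on escalation between cohorts. The review period ends at "the time that the final subject enrolled in the cohort(s) has completed 7 days of safety follow-up".
- **Event-driven safeguards (Sections 4.4.1 and 4.8.5).** Listed events halt dosing. Events under criteria 1 to 4 "must be reported within 24 hours of knowledge of the event"; those that might meet criteria 5 and 6 go to the site monitor and the eCRF within 24 hours of awareness. The ESMC also reviews events that meet a stopping criterion, or that the medical monitor or an investigator judges medically relevant.

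**The concern.** In a first-in-human trial, the purpose of dosing five subjects ahead of the rest is to learn from them before exposing the others. An interval does that only if someone asks the five how they are before it ends. Here the interval and the call are set independently, and the call window extends past the interval.

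The safeguards that run in the meantime depend on someone becoming aware of an event. Fatigue or myalgia that prevents daily activity is Grade 3 in Appendix 4, yet a subject may neither telephone about it nor seek care. Diary cards cover Days 1 to 7 (Section 5.8), but nothing requires them to be read before release. Under Section 5.8, solicited symptoms are not assessed for relationship, so such a symptom counts towards stopping criterion 5 only if the investigator also records it as an adverse event and judges it related. T3 is the first scheduled occasion after Day 1 for that judgment.

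**Working it through.** No power or sample-size figure is in dispute. The check is one of study-day arithmetic.

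**1. The plan's own counts.** 5 + 19 = 24 per cohort, as in Table 3.1.2-1; 6 × 24 = 144. Subjects dosed under the release rule: 6 × 19 = 114 of 144. This counts subjects governed by the rule, not subjects expected to be affected.

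**2. Earliest release.** Three days elapsed: Day 1 + 3 = Day 4. Three clear days between: Day 1 + 4 = Day 5.

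**3. T3 window.** Day 3 to Day 3 + 3 = Days 3, 4, 5 and 6.

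**4. Compliant T3 days that fall after the earliest release.** Let *k* be the number of days by which a subject was dosed before the last of the initial five, with the interval counted from that last subject. At release this subject is at Day 4 + *k* (or Day 5 + *k*).

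| *k* | Release on Day 4 of last subject | Release on Day 5 of last subject |
|---|---|---|
| 0 | Days 5 and 6 | Day 6 |
| 1 | Day 6 | none (Day 6 is the same day) |
| 2 | none (Day 6 is the same day) | none |
| 3 or more | none | none |

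The gap exists on both readings of the 3-day rule. It is widest for subjects dosed on the same day as the last of the five. A T3 call on Day 3 precedes release in every row.

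**5. Next contact.** The Day 8 visit falls on Days 8 to 11, which is 8 − 4 = 4 to 11 − 4 = 7 days after a Day 4 release. It cannot stand in for T3.

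**6. What an earlier call could change.** Criterion 5 is met by one related Grade 4 event, or by two related Grade 3 events of the same type in more than one subject of a cohort. One silent Grade 3 symptom among the five does not meet it. Two subjects with the same related Grade 3 event would, and five subjects can produce that pair. A call could also reveal a finding that leads the investigators, sponsor or ESMC to invoke criterion 6, which is a matter of judgment.

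**The case against.** The strongest reply is that nothing here is misstated. T3 is nominally Day 3 and release is Day 4 at the earliest, so on the nominal schedule all five are asked first. The 3 days are a minimum, and sites may wait longer. This stands: the gap is permitted rather than inevitable, and the documents give no rate of late calls from which to judge its likelihood.

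A reader might infer that an unreported Grade 3 reaction in one of the five means a missed stop. The documents do not support that, because criterion 5 needs a matching pair in two subjects, both recorded as adverse events and judged related. For fatigue, myalgia, headache, pain and tenderness, Grade 4 is defined by an emergency room visit or hospitalization, so those events are less likely to stay silent.

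A reader might also infer that the first five are unmonitored between Day 1 and T3. They are not. They are observed after dosing and have the investigator's contact details, and a medical monitor can be reached at any hour through their physician (Section 6.5). The stopping rules run throughout, and the ESMC can be asked to look at any medically relevant event. A late call can still protect those of the 19 not yet dosed. Each adjuvanted dose also follows committee review of the same antigen dose given alone.

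Finally, the ESMC charter and Figure 3.1.1-1 could not be seen and might contain a within-cohort check. It therefore cannot be said that the trial has none, only that Section 3.1.2, which Section 3.1.1 cites for the stagger, does not require one.

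**Conclusion.** The point holds as a gap in a stated safety rule. Section 3.1.2 allows the final 19 to be dosed before the initial five have had any scheduled enquiry after Day 1. Compliant calls can fall 1 to 2 days after a Day 4 release (5 − 4 and 6 − 4), or 1 day after a Day 5 release (6 − 5). The result rests on the day count in Section 4.5.1.2, the T3 window in Section 4.2.2.2 and use of the minimum interval. It needs no assumption about event rates.

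It does not show that any stopping event would be missed, and it touches no statistical figure. It is worth correcting because the call is already scheduled, the change is small, and T3 is the first planned occasion to detect a pair of Grade 3 events or a finding relevant to criterion 6.

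**What to change.** State in Section 3.1.2 that the final group may not be dosed until both conditions hold:

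- at least 3 days have passed since the last of the initial five was dosed;
- a T3 contact, targeted for Day 3 or 4, has been completed for each of the five, and no Section 4.4.1 criterion is met on the information obtained.

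If a subject cannot be reached by Day 6, the medical monitor decides on release and documents the decision. This leaves room for release without contact, but as a recorded exception rather than a default. Add a matching footnote to T3 in Table 4.2.2-1.

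**Cost.** No extra visit or call is needed. There is no delay if all five calls are made by Day 3, or on Day 4 before dosing starts. Taking release on the day of the latest call or the day after, and comparing with a Day 4 release, a Day 5 call costs 1 to 2 days and a Day 6 call 2 to 3 days per cohort step. Over the four sequential steps (1; 1a with 2; 2a with 3; 3a), Day 6 calls every time would cost 4 × 2 = 8 to 4 × 3 = 12 days. On the clear-days reading, a Day 6 call costs 1 to 2 days per step, or 4 to 8 days in all. A longer delay arises only if a subject is unreachable and the medical monitor withholds release.
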